## **7.3 Addendum 3: HIV-Related Events or Outcomes**

### **7.3.1 CLINICAL CATEGORIESa**

The clinical categories of HIV infection are defined as follows.

#### **7.3.1.1 Category A**

Category A consists of 1 or more of the conditions listed below in an adolescent or adult ( $\geq 13$  years) with documented HIV infection. Conditions listed in Categories B and C must not have occurred.

- Asymptomatic HIV infection
- Persistent generalized lymphadenopathy
- Acute (primary) HIV infection with accompanying illness or history of acute HIV infection

#### **7.3.1.2 Category B (Symptomatic Non-AIDS Conditions)**

Category B consists of symptomatic conditions in an HIV-infected adolescent or adult that are not included among conditions listed in clinical Category C, and that meet at least 1 of the following criteria: a) the conditions are attributed to HIV infection or are indicative of a defect in cell-mediated immunity; or b) the conditions are considered by physicians to have a clinical course or to require management that is complicated by HIV infection. Examples of conditions in clinical category B include, but are not limited to the following.

- Bacillary angiomatosis
- Candidiasis, oropharyngeal (thrush)
- Candidiasis, vulvovaginal; persistent, frequent, or poorly responsive to therapy
- Cervical dysplasia (moderate or severe)/cervical carcinoma in situ
- Constitutional symptoms, such as fever ( $38.5^{\circ}\text{C}$ ) or diarrhea lasting  $> 1$  month
- Hairy leukoplakia, oral
- Herpes zoster (shingles), involving at least 2 distinct episodes or more than one dermatome;
- Idiopathic thrombocytopenic purpura
- Listeriosis
- Pelvic inflammatory disease, particularly if complicated by tubo-ovarian absces;
- Peripheral neuropathy

For classification purposes, Category B conditions take precedence over those in Category A. For example, someone previously treated for oral or persistent vaginal candidiasis (and who has not developed a Category C disease) but who is now asymptomatic should be classified in clinical Category B.

---

a 1993 revised classification system for HIV infection and expanded surveillance case definition for AIDS among adolescents and adults. MMWR 1992; 41 (RR-17): 1-19.

The following list of other non-CDC HIV-associated conditions was compiled, as the CDC notes that Category B is not limited to events listed in the CDC 1993 definition.

- Aspergillosis
- Leishmaniasis
- Microsporidiosis
- Molluscum contagiosum
- Nocardiasis
- Thrombotic microangiopathy (haemolytic uremic syndrome [HUS]/thrombotic thrombocytopenia purpura [TTP])

### **7.3.1.3 Category C (AIDS Indicator Conditions as Defined by Diagnostic or Presumptive Measures)**

Category C includes the clinical conditions listed in the AIDS surveillance case definition. For classification purposes, once a Category C condition has occurred, the person will remain in Category C. Conditions in Category C include the following.

- Candidiasis of bronchi, trachea, or lungs
- Candidiasis, oesophageal
- Cervical cancer, invasive
- Coccidiomycosis, disseminated or extrapulmonary
- Cryptococcosis, extrapulmonary
- Cryptosporidiosis, chronic intestinal (> 1 month's duration)
- Cytomegalovirus disease (other than liver, spleen or nodes)
- Cytomegalovirus retinitis (with loss of vision)
- Encephalopathy, HIV-related
- Herpes simplex: chronic ulcer(s) (> 1 month's duration); or bronchitis, pneumonitis, or oesophagitis
- Histoplasmosis, disseminated or extrapulmonary
- Isosporiasis, chronic intestinal (> 1 month's duration)
- Kaposi's sarcoma
- Lymphoma, Burkitt's (or equivalent term)
- Lymphoma, immunoblastic (or equivalent term)
- Lymphoma, primary, or brain
- Mycobacterium avium complex or M. kansasii, disseminated or extrapulmonary
- Mycobacterium tuberculosis, any site (pulmonary or extrapulmonary)
- Mycobacterium, other species or unidentified species, disseminated or extrapulmonary
- Pneumocystis carinii pneumonia
- Pneumonia, recurrent

- Progressive multifocal leukoencephalopathy
- Salmonella septicaemia, recurrent
- Toxoplasmosis of brain
- Wasting syndrome due to HIV

## 7.4 Addendum 4: Visit Schedule for Rash Management in Pediatric Patients

This visit schedule summarizes the visits and assessments to be performed in case of rash. At the investigator's discretion, additional visits and assessments can be performed.

|                          | Grade 1 Rash   | Grade 2 Rash   | Grade 3 or 4 Rash   |
|--------------------------|---|---|--|
| Day 0a | 
 
Study medication MAY be CONTINUED.
 
Unscheduled visit for initial rash evaluation REQUIRED.
 
Referral to dermatologist ONLY IF rash diagnosis uncertain (within 24h).
 
 | 
 
Study medication MAY be CONTINUED.
 
Unscheduled visit for initial rash evaluation REQUIRED.
 
Referral to dermatologist REQUIRED (within 24h).
 
Assessment of safety blood sample by local laboratory ONLY IF requested by investigator or dermatologist.
 
Biopsy ONLY IF required by dermatologist.
 
 | 
 
Study medication MUST be permanently DISCONTINUED. Rechallenge is NOT ALLOWED.
 
Unscheduled visit for initial rash evaluation REQUIRED.
 
Referral to dermatologist REQUIRED (within 24h).
 
Assessment of safety blood sample by local laboratory ONLY IF requested by investigator or dermatologist.
 
Biopsy ONLY IF required by dermatologist.
 
 |
| Day 1             | 
 
Follow-up visit REQUIRED.
 
Digital pictures REQUIRED.
 
   | 
 
Follow-up visit REQUIRED.
 
  | 
 
Follow-up visit REQUIRED.
 
   |
| Day 2             | No Rash follow-up visit required b   | No Rash follow-up visit required b   | 
 
Follow-up visit REQUIRED.
 
Assessment of safety blood sample by local laboratory ONLY IF requested by investigator or dermatologist.
 
   |
| Day 3             | No Rash follow-up visit required b   | No Rash follow-up visit required b   | 
 
Follow-up visit REQUIRED.
 
Assessment of safety blood sample by local laboratory ONLY IF requested by investigator or dermatologist.
 
   |

a Note that Day 0 of the rash is the first day of investigator assessment and not the first day of rash as reported by the subject.

b In case rash progresses from a grade 1 or a grade 2 to a higher grade, start follow-up schedule for grade 2, 3 or 4 rash as appropriate.

|                       | Grade 1 Rash   | Grade 2 Rash   | Grade 3 or 4 Rash   |
|-----------------------|---|---|--|
| Day 4          | No Rash follow-up visit required b   | No Rash follow-up visit required b   | 
 
• Follow-up visit REQUIRED.
 
• Assessment of safety blood sample by local laboratory ONLY IF requested by investigator or dermatologist.
 
 |
| Day 5          | No Rash follow-up visit required b   | No Rash follow-up visit required b   | 
 
• Follow-up visit REQUIRED.
 
• Assessment of safety blood sample by local laboratory ONLY IF requested by investigator or dermatologist.
 
 |
| Day 6          | No Rash follow-up visit required b   | No Rash follow-up visit required b   | No Rash follow-up visit required   |
| Day 7          | 
 
• Follow-up visit REQUIRED.b
 
                  | 
 
• Follow-up visit REQUIRED.b
 
• Digital pictures REQUIRED.
 
 | No Rash follow-up visit required   |
| Further Visits | If rash is unresolved after second follow-up visit, further visits at the investigator's discretion. b | If rash is unresolved after second follow-up visit, further visits at the investigator's discretion. b                             | Weekly follow-up visits REQUIRED until resolution of grade 3-4 rash to grade $\leq$ 2 rash (further follow-up visits according to grade 1 or grade 2 rash instructions).                                  |

b In case rash progresses from a grade 1 or a grade 2 to a higher grade, start follow-up schedule for grade 2, 3 or 4 rash as appropriate.

## 7.5 Addendum 5: Visit Schedule for Rash Management in Adult Patients

This visit schedule summarizes the visits and assessments to be performed in case of rash. At the investigator's discretion, additional visits and assessments can be performed.

|                    | Grade 1 Rash   | Grade 2 Rash  | Grade 3 or 4 Rash   |
|--------------------|--|---|---|
| Day 0  | 
 
Study medication MAY be CONTINUED.
 
Unscheduled visit for initial rash evaluation REQUIRED.
 
 | 
 
Study medication MAY be CONTINUED.
 
Unscheduled visit for initial rash evaluation REQUIRED.
 
Assessment of safety blood sample by local laboratory OPTIONAL.
 
Referral to dermatologist OPTIONAL (within 24h).
 
 | 
 
Study medication MUST be permanently DISCONTINUED. Rechallenge is NOT ALLOWED.
 
Unscheduled visit for initial rash evaluation REQUIRED.
 
Assessment of safety blood sample by local laboratory REQUIRED.
 
Digital pictures OPTIONAL (within 24h).
 
Referral to dermatologist REQUIRED (within 24h).
 
Biopsy REQUIRED for Grade 4 rash (within 24h). Biopsy at the dermatologist's discretion for Grade 3 rash.
 
 |
| Day 1              | 
 
Follow-up visit REQUIRED.
 
   | 
 
Follow-up visit REQUIRED.
 
Assessment of safety blood sample by local laboratory OPTIONAL.
 
  | 
 
Follow-up visit REQUIRED.
 
Assessment of safety blood sample by local laboratory REQUIRED.
 
Digital pictures OPTIONAL.
 
   |
| Day 2              | No Rash follow-up visit required   | No Rash follow-up visit required    | 
 
Follow-up visit REQUIRED.
 
Assessment of safety blood sample by local laboratory REQUIRED only if on Days 0 and/or 1 of rash AST/ALT > 2 x baseline value, AND/OR ≥ 5 x ULN, AND/OR in case of rash progression.
 
Digital pictures OPTIONAL.
 
   |

 Note that Day 0 of the rash is the first day of investigator assessment and not the first day of rash as reported by the subject.

 In case rash progresses from a grade 1 or a grade 2 to a higher grade, start follow-up schedule for grade 2, 3 or 4 rash as appropriate.

|                       |   |  |   |
|-----------------------|---|--|---|
| Day 3          | No Rash follow-up visit required    | No Rash follow-up visit required   | 
 
Follow-up visit REQUIRED.
 
Assessment of safety blood sample by local laboratory REQUIRED only if on Days 0 and/or 1 of rash AST/ALT > 2 x baseline value, AND/OR <math>\geq 5</math> x ULN, AND/OR in case of rash progression.
 
Digital pictures OPTIONAL
 
   |
| Day 4          | No Rash follow-up visit required    | No Rash follow-up visit required   | 
 
Follow-up visit REQUIRED.
 
Assessment of safety blood sample by local laboratory REQUIRED only if on Days 0 and/or 1 of rash AST/ALT > 2 x baseline value, AND/OR <math>\geq 5</math> x ULN, AND/OR in case of rash progression.
 
Digital pictures OPTIONAL
 
   |
| Day 5          | No Rash follow-up visit required    | No Rash follow-up visit required   | 
 
Follow-up visit REQUIRED.
 
Assessment of safety blood sample by local laboratory REQUIRED.
 
Digital pictures OPTIONAL.
 
   |
| Day 6          | No Rash follow-up visit required    | No Rash follow-up visit required   | No Rash follow-up visit required  |
| Day 7          | 
 
Follow-up visit REQUIRED.
 
                    | 
 
Follow-up visit REQUIRED.
 
Assessment of safety blood sample by local laboratory OPTIONAL.
 
 | No Rash follow-up visit required  |
| Further Visits | If rash is unresolved after second follow-up visit, further visits at the investigator's discretion.  | If rash is unresolved after second follow-up visit, further visits at the investigator's discretion.   | 
 
Weekly follow-up visits REQUIRED until resolution of grade 3-4 rash to grade <math>\leq 2</math> rash (further follow-up visits according to grade 1 or grade 2 rash instructions)
 
Weekly assessment of safety blood sample by local laboratory REQUIRED as long as grade 3 or 4 rash is present but only if on Day 5 of rash AST/ALT > 2 x baseline value, AND/OR <math>\geq 5</math> x ULN, AND/OR in case of rash progression, until resolution of AST/ALT abnormalities.
 
 |

 In case rash progresses from a grade 1 or a grade 2 to a higher grade, start follow-up schedule for grade 2, 3 or 4 rash as appropriate.

|  |  |  |  |
|--|--|--|--|
|  |  |  | 

• Digital pictures OPTIONAL

 |
| Upon Rash Resolution/
Stabilization |  |  | Take digital pictures ( OPTIONAL ).   |

---

 Stabilization: to be agreed upon in collaboration with the sponsor.

## **PART II: PROCEDURES**

### **1 ADVERSE EVENTS**

#### **1.1 Definitions**

##### **ADVERSE EVENT (AE)**

Any untoward medical occurrence in a patient or clinical investigation subject administered a pharmaceutical product and which does not necessarily have a causal relationship with this treatment. An adverse event can therefore be any unfavourable and unintended sign (including an abnormal laboratory finding), symptom, or disease temporally associated with the use of a medicinal (investigational) product, whether or not related to the medicinal (investigational) product (International Conference on Harmonization - ICH E6; 1.2).

##### **SERIOUS ADVERSE EVENT (SAE)**

Any untoward medical occurrence that at any dose:

- results in death;
- is life threatening;
- requires inpatient hospitalization or prolongation of existing hospitalization;
- results in persistent or significant disability/incapacity;

or

- is a congenital anomaly/birth defect (ICH E6; 1.50).

##### Note

- Medical and scientific judgment should be exercised in deciding whether expedited reporting is appropriate in other situations, such as important medical events that may not be immediately life threatening or result in death or hospitalization, but may jeopardize the subject or may require intervention to prevent 1 of the outcomes listed in the definition above.
- Hospitalizations that were planned prior to the signing of C/assent, and where the underlying condition for which the hospitalization was planned has not worsened, will not be considered serious adverse events. Any adverse event that results in a prolongation of the originally planned hospitalization is to be reported as a new serious adverse event.
- For convenience the investigator may choose to hospitalize the subject for the duration of the treatment period; this will not be considered as a serious adverse event.

##### **UNLISTED (UNEXPECTED) ADVERSE EVENT**

An adverse reaction, the nature or severity of which is not consistent with the applicable product information (e.g., Investigator's Brochure for an unapproved investigational product or package insert/summary of product characteristics for an approved product).

**LIFE THREATENING**

An event in which the subject was at risk of death at the time of the event; it does not refer to an event, which hypothetically might have caused death if it were more severe.

**ASSOCIATED WITH THE USE OF THE DRUG**

An adverse event is considered associated with the use of the drug if the attribution is possible, probable or very likely.

**1.2 Attribution Definitions****NOT RELATED**

An adverse event, which is not related to the use of the drug.

**DOUBTFUL**

An adverse event for which an alternative explanation is more likely, e.g., concomitant drug(s) or concomitant disease(s), and/or the relationship in time suggests that a causal relationship is unlikely.

**POSSIBLE**

An adverse event, which might be due to the use of the drug. An alternative explanation, e.g., concomitant drug(s) or concomitant disease(s), is inconclusive. The relationship in time is reasonable; therefore the causal relationship cannot be excluded.

**PROBABLE**

An adverse event, which might be due to the use of the drug. The relationship in time is suggestive, e.g., confirmed by dechallenge. An alternative explanation is less likely, e.g., concomitant drug(s) or concomitant disease(s).

**VERY LIKELY**

An adverse event, which is listed as a possible adverse reaction and cannot be reasonably explained by an alternative explanation, e.g., concomitant drug(s) or concomitant disease(s). The relationship in time is very suggestive (e.g., it is confirmed by dechallenge and rechallenge).

**1.3 HIV-Related Events or Outcomes**

The events or outcomes listed in the classification list (see Part I, Section 7.3, Addendum 5) are to be recorded as HIV-related events on the CRF. These events or outcomes, as well as any sign, symptom, diagnosis, illness, and/or clinical laboratory abnormalities that can be linked to any of these events or outcomes, are not to be reported as an adverse event.

After termination of data collection (see Figure 1), safety will continue to be assessed per local standard of care and documented in the subject's medical records only. Data will no longer be recorded in the CRF. Investigators will continue to report SAEs possibly related to ETR and pregnancies to the sponsor using regular pharmacovigilance reporting. This information will only be entered in the company safety repository.

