#### **5.7.3.1 Safety**

The safety of ETR will be summarized in terms of:

- Mortality
- All SAEs
- AEs leading to discontinuation
- AEs possibly related to ETR treatment

The number of and causes of deaths will be summarized.

The number of subjects who terminate treatment will be tabulated, and reasons for drug discontinuation will be summarized.

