## 1.4 Reporting of Adverse Events

Adverse events considered to be at least possibly related to ETR treatment, adverse events leading to treatment interruption or discontinuation, serious adverse events and pregnancies are to be collected from the signing of ICF/assent onwards. All other adverse events that do not meet criteria for seriousness are only to be collected if required per local regulations. Occurrence of adverse events is to be reported in the Adverse Event section of the CRF.

All reportable adverse events and adverse events leading to treatment interruption or discontinuation still ongoing at the end of the treatment are to be followed by the investigator according to the local standard of care.

New adverse events considered to be at least possibly related to ETR treatment, adverse events leading to treatment interruption or discontinuation, and serious adverse events reported during the follow-up period of the trial are to be followed as agreed between the sponsor and investigator.

Certain long-term adverse events of antiretroviral therapy cannot be followed until resolution within the setting of this protocol; in these cases follow-up is the responsibility of the treating physician. However, this has to be agreed upon with the sponsor.

Serious adverse events occurring within the clinical trial (between signing of C/assent and last follow-up visit) are to be reported. Any SAEs with at least a possible relationship to the study medication occurring after the end of the trial must be reported, and are to be handled by the sponsor.

The start date of the serious adverse event documented on the Serious Adverse Event form must be the same as the start date of the corresponding adverse event documented on the CRF. If a change in severity is noted for the existing adverse event, it must be recorded as a new adverse event. If a worsened adverse event meets the criteria for a serious adverse event, the start date of the serious adverse event must be the same as the start date of the worsened adverse event.

The cause of death of a subject in a clinical trial, whether the event is expected or associated with the investigational agent, is a serious adverse event.

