**All serious adverse events and pregnancies occurring during clinical trials must be reported to the Drug Safety Officer as specified on the Serious Adverse Event Form immediately (i.e., within 24 hours) after the investigator becoming aware of the event. For the names and phone numbers of the contact person(s) see Part I, Section 7.1, Addendum 1.**

The first report of a serious adverse event may be made by telephone or facsimile (FAX). The investigator must provide the minimal information: i.e., trial number, subject's initials and date of birth, medication code number, period of intake, nature of the adverse event, and investigator's attribution.

This report of a serious adverse event by telephone must always be confirmed by a written, more detailed report. For this purpose, the monitor provides the investigator with a Serious Adverse Event Form, to be completed and signed by the latter. If initial reporting was done by telephone, the person answering the phone can complete the Serious Adverse Event Form according to the information provided by the investigator. This form needs to be reviewed, completed if applicable, signed, and dated for approval by the investigator.

Pregnancies occurring during clinical trials are considered immediately reportable events. They must be reported as soon as possible using the same Serious Adverse Event Form. The outcome of the pregnancy must also be reported to the Drug Safety Officer.

The sponsor or its representatives assumes responsibility for appropriate reporting of adverse events to Regulatory Authorities. Adverse Events reporting, including suspected unexpected serious adverse reactions, is to be carried out in accordance with applicable local regulations. For reported deaths, the investigator should supply the sponsor and the IEC/IRB with any additional requested information (e.g., autopsy reports and terminal medical reports).

After termination of the clinical trial (last subject last visit in the trial), any unexpected safety issue that changes the risks benefit analysis and is likely to have an impact on the subjects who have participated in it, should be reported as soon as possible to the competent authority(ies) concerned together with proposed actions.

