## **5 REPORTING AND PUBLICATION**

### **5.1 Reporting**

The sponsor will create an Annual Safety Report (ASR) and Line Listings in accordance with the EU Clinical Trials Directive with a data-lock date of 27-MAR. This study TMC125-C239 will be included in the first ASR produced after approval of this protocol, which may be less than 1-year's time from this particular study approval date, and in all subsequent ASRs, as appropriate, until study closure.

The results of the trial will be reported in a CSR and will contain CRF data from all study sites that participated in the study. A summary of the Clinical Study Report will be provided to the investigators, to the applicable regulatory authorities, and IECs/IRBs, if required by the applicable regulatory requirements, within 1 year after end of trial.

After termination of data collection (see [Figure 1](#)), only limited safety data (SAEs possibly related to ETR and pregnancies) will continue to be reported using regular pharmacovigilance reporting and will only be entered in the company safety repository. Appropriate safety reports will continue to be provided to IECs/IRBs and regulatory authorities, as required.

One investigator will be appointed for signing off the final CSR. The selection of this investigator will be determined by the recruitment performance and specific expertise related to the nature and the key assessment parameter(s).

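### Non-fatal events recorded only as HIV-related can drop out of the SAE, related-AE and discontinuation outputs, and the SAP shows them nowhere else except in one pooled disposition reason

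*Protocol*

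**What the plan says.** Part II 1.3 of the protocol has the conditions in Section 7.3 recorded on the CRF as HIV-related events. It then removes them from AE reporting, together with associated findings of any kind: "clinical laboratory abnormalities that can be linked to any of these events or outcomes, are not to be reported as an adverse event". No exception is made for cases that are serious, possibly caused by ETR, or the reason for stopping ETR.

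Part II 1.4 asks for exactly those three classes in the AE section of the CRF and makes no exception for HIV-related events. On seriousness it says: "Serious adverse events occurring within the clinical trial (between signing of C/assent and last follow-up visit) are to be reported". It adds that "All serious adverse events and pregnancies occurring during clinical trials must be reported to the Drug Safety Officer", within 24 hours, and that the start date on the SAE Form "must be the same as the start date of the corresponding adverse event documented on the CRF". A subject's cause of death, "whether the event is expected or associated with the investigational agent, is a serious adverse event".

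On analysis, Protocol 5.7.3.1 states: "The safety of ETR will be summarized in terms of" mortality, all SAEs, AEs leading to discontinuation and AEs possibly related to ETR. Part II 5.1 says that the trial results "will be reported in a CSR and will contain CRF data from all study sites". SAP 7.1 codes the terms that investigators entered in the CRF to name adverse events and analyses all reported AEs. The SAP mentions HIV-related events once, in 5.2, where they share a single disposition reason with AEs, cutaneous events and rash.

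**The concern.** Efficacy is not analysed (SAP 6), so safety is the main content of the report. Three of its promised components (SAEs, related AEs and AEs leading to discontinuation) are built from CRF adverse event records. If sites follow 1.3 as worded, some of the events those tables are meant to count never enter those records. If some sites follow 1.3 and others follow 1.4, the same clinical event is counted at one site and not at another. A reader of the study report could not then tell whether a low count reflects few events or the recording rule.

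**Working it through.** No figure in the plan depends on this point, so the check is a comparison of texts and a count of outputs.

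1. **Does either section yield to the other?** No. Neither 1.3 nor 1.4 refers to the other on this question. The SAE definition in Part II 1.1 has no HIV-related carve-out. Protocol 5.4.3.1 adds only that further details are recorded for AIDS-defining illnesses; it is silent on seriousness, causality and stopping treatment. The second paragraph of 1.3 says "Investigators will continue to report SAEs possibly related to ETR and pregnancies to the sponsor using regular pharmacovigilance reporting", but it describes the period after CRF collection ends. It is not worded as an exception to the bar, and it feeds only the company safety repository.

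2. **Can 1.4 simply be assumed to win?** Not safely. Under 1.4, AEs that are non-serious, unrelated to ETR and without effect on treatment are collected only where local regulations require it. If 1.4 overrode 1.3 for all three mandatory classes, the bar in 1.3 would have effect only in that residual group. This does not show which reading was meant, but it does show that a site could reasonably apply 1.3 to serious cases.

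3. **Follow one hypothetical case.** A subject is hospitalised with a listed condition, survives, and stops ETR because of it.
   - Under 1.3, the CRF holds an HIV-related event and no AE.
   - Under 1.4, an SAE Form still goes to the Drug Safety Officer. Its start date has to match a CRF adverse event that, under 1.3, does not exist.
   - Under SAP 7.1, there is no AE term to code, so the case is absent from TSFAE03 and LSFAE03 (serious) and from TSFAE06 and LSFAE06 (permanent stop). Had it been judged possibly related, it would also be absent from TSFAE05 and LSFAE04. TSFAE02 and LSFAE01 draw on the same AE records and would not recover it.
   - In TDIS01 and LDIS01 the subject falls under the pooled reason. The disposition table then counts a stop that the AE discontinuation table lacks, and nothing explains the difference.

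4. **Count the outputs in SAP 7.3.** COVID 2 + demographics 2 + antiretroviral therapies 3 + disposition 2 + AE tables 7 + AE listings 6 + weight tables 2 + weight listings 2 = 26. Outputs naming HIV-related events: 0. AE outputs: 7 + 6 = 13. Those restricted to the three classes at issue: TSFAE03, TSFAE05, TSFAE06, LSFAE03, LSFAE04 and LSFAE06, which is 6 of 13.

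**The case against.** The best defence is that safety reporting itself is sound. The bar in 1.3 speaks of adverse events and never mentions the SAE Form. The SAE definition is general, and 1.4 demands expedited reporting of every SAE. The start-date rule can even be read as implying that serious cases belong in the AE section. This largely stands. A reader might infer that serious HIV-related events go unreported to the sponsor; the documents do not support that. What is left is a gap in the CRF-based tables, not in pharmacovigilance.

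A reader might also infer that fatal HIV-related events vanish from the report. They should not. Protocol 5.7.3.1 promises the number and causes of deaths, SAP 7.1 promises a mortality summary and a mortality listing, and 1.4 makes the cause of death an SAE. SAP 7.3 has no output titled for mortality, but it is an overview, and a missing title there does not cancel 7.1.

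It is also fair to say that the protocol never promised a table of HIV-related events and that this is an access trial with no hypothesis. That is true, but it does not answer the point: the protocol did promise summaries of all SAEs, of AEs leading to discontinuation and of possibly related AEs, and 1.3 as worded can make those incomplete.

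Finally, the effect depends on CRF pages that are not in the documents and on what sites actually did. This stands and limits the claim. The length of the condition list is no guide to frequency either: it includes asymptomatic HIV infection, in a trial that enrols only people with HIV-1.

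**Conclusion.** The point holds in a limited form. Part II 1.3 and 1.4 give conflicting instructions for non-fatal HIV-related events that are serious, possibly related to ETR or treatment-ending. Where 1.3 is followed literally, those events are absent from six AE outputs, and the only other trace in the planned outputs is the pooled disposition reason. The number of events affected is unknown and may be zero if sites entered such cases as AEs anyway. The conclusion assumes that the AE outputs are built from the CRF adverse event records alone, as SAP 7.1 and Part II 5.1 indicate. It is worth correcting before the final analysis because the remedy is cheap and uses data that the protocol already sends to the CRF.

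**What to change.** **SAP 7.1 and 7.3.** Add one table and one listing of CRF-recorded HIV-related events, by adult and pediatric group, and by CDC category where it applies (Categories A and B are worded for adolescents and adults). Cross-check these events against the SAE, death and disposition records. Footnote TSFAE03, TSFAE05 and TSFAE06 to say that events recorded only as HIV-related are shown in the new outputs. In those outputs, flag cases that were serious, possibly related or treatment-ending wherever the CRF or SAE Form records this.

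**Protocol.** Reconcile Part II 1.3 with 1.4 so that one rule is stated for these cases. As a clerical matter, 1.3 cites the condition list as Addendum 5; Section 7.3 is Addendum 3.

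**Cost.** Slight extra programming: one table, one listing, three footnotes and a cross-check. The cross-check can go no further than what the CRF and SAE Forms hold. The protocol edit does little for future data, because under Amendment 3 CRF collection stops at the Final/Withdrawal Visit and no statistical analysis follows the end of data collection. Most of the benefit therefore comes from the SAP change.
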